7.3 Safety Follow up

Adverse events and device deficiencies will be assessed at all visits, planned and unplanned. Subjects are followed through termination of the investigation (Visit 2). Any ongoing ADEs or SADEs at study termination will be followed until resolution. All subjects are encouraged to contact the Principal Investigator, or designee, if they experience problems that they believe are related to their investigational product or participation. This is to ensure that any device-related events are documented and to safeguard the subjects' health.

7.4 Schedule of assessments

Table 7-1 Schedule of assessments

	Day 0			Day 2			
Procedures	VO	V1-1	V1-2 (Cystoscopy)	V2- 1	V2-2 (1 catheterization: 6 x repositioning)	V2-3	V2-4 (Cystoscopy)
Informed consent (Allocation of Subject Number in EDC)	x				15	*(
Inclusion/Exclusion criteria	-	X					
Randomization		Х					
Demographics & Baseline Data Collected		x					
Urine sample -Dipstick haematuria -Dipstick pregnancy test (pregnancy test only at V1-1)		x	*	×	e = *	×	
RBC				Х		X	
WBC				Х		X	
Cystoscopy Imaging			Х				X
Bladder Assessment							X
Volume of Urine recorded			a l	x		x	
Pre-catheterization Residual Volume					X		
Visualization of blood	×		X		X		Х
Adverse Events	Х	Χ	Х	Х	X	Х	X
Concomitant Medications	х	х	х	х	X	х	х
Device Deficiencies				7-	X	Х	X

7.5 Concomitant Medications

Concomitant medications will be registered in the eCRF. All concomitant medications the subject has taken from the time of consent through study termination will be collected.

7.6 Prohibitive Medications/Treatments

There are no prohibitive medications in this study.

8 Risk-benefit analysis and ethical considerations

8.1 Risk-benefit analysis of the investigational device

A risk analysis according to ISO 14971 Application of risk management to medical devices has been conducted. Risks have been proven minimized or eliminated through appropriate design control, confirmed by pre-clinical bench, and laboratory testing.

The risk management process has been performed in accordance with the requirements stated in ISO 14971:2012 and in accordance with internal Coloplast procedures, including design verification, validated test methods, risk analysis and completion of a biological evaluation report for the test product.

To mitigate and reduce the risks, the site personnel will be trained, according to the IFU.

The investigation is conducted in accordance with current applicable standards. Please refer to section 15, Statement of compliance. The rights, safety and well-being of human subjects shall prevail over the interest of science.

Risks have been proven minimized or eliminated through appropriate design control, confirmed by pre-clinical bench, and laboratory studies.

8.2 Risk-benefit analysis for the conduct of the clinical investigation

The participating subjects will contribute with important information for the development of new intermittent catheters, that may reduce bladder complications; specifically, mucosal microtrauma associated with the conventional eyelet catheters. Due to the actions taken to mitigate any risks, the risks and disadvantages when participating in this clinical investigation are estimated as low. The subject's health will not benefit directly from this investigation.

8.3 Delegation of responsibility

Qualified site personnel can perform investigational related tasks per the Principal Investigator's (PI) delegation. This delegation must be documented in the 'Site Personal Signature and Delegation List' for each site. All Principal Investigators and designees will receive training in all aspects of the investigation and before they can begin any investigational related tasks. The training must be documented in the 'Clinical Investigation Training Log' at each site. The Principal Investigator is responsible for maintaining these logs.

9 Monitoring

The sponsor is responsible for ensuring appropriate monitoring of the clinical investigation activities. A study-specific monitoring plan has been developed and includes details regarding the monitoring strategy (i.e., on-site, remote, and centralized).

The monitors will be the primary contact for the Principal Investigator and clinical investigation site personnel.

Monitoring activities are mandatory as per good clinical practice; however, the extent and depth of these activities depend on the criticality of the clinical investigation, speed of enrolment, the experience of the clinical investigation site personnel in carrying out clinical investigations and specific study designs.

For this clinical investigation, the below described monitoring procedures have been determined.

The data collected throughout the investigation, and the conduct of the investigation, will be monitored per the monitoring plan to ensure, and verify, that the rights and well-being of the subjects are protected, that the reported data are accurate, complete, and verifiable from source documents, and that the conduct of the investigation complies with the approved CIP, subsequent amendment(s), ISO14155 and the applicable regulatory requirements.

The monitoring process is briefly described below and detailed in the Monitoring Plan. The monitoring will be conducted per the monitoring plan by qualified designee personnel.

The investigator must be available for and agrees to cooperate with Coloplast Clinical Managers (CM) and/or the Clinical Research Associates (CRA) during their visits and ensure that they have direct access to all documents that they require, including direct access to the subjects' files.

The investigation will be subject to internal audits if relevant. All monitoring visits and possible audits will be followed by internal reports and corrective actions, if needed. Follow-up letters will be forwarded to sites after all visits and any findings should be addressed by the investigator or designee.

To ensure proper conduct of the investigation the following visits on site will be performed during the investigation:

- Site selection visit
- Site Initiation Visit
- Periodic Monitoring visits
- Close Out visit

9.1 Site Selection visit

Depending on the prospective clinical investigation site's experience with the specific investigational device, an on-site qualification or site selection visit shall be performed during which the feasibility of the clinical investigation requirements will be discussed and common agreement between sponsor and principal investigator shall be reached. This visit may also be replaced by one or more phone calls if the Principal Investigator is known to the sponsor.

9.2 Site Initiation visit

The clinical investigation site will get an initiation visit during which full training on all aspects of the clinical investigation will be provided. This visit will be done on-site or remotely.

9.3 Site Monitoring visit(s)

The site dedicated monitor is to ensure adherence to the clinical investigation plan, accurate data recording on the eCRFs and to monitor recruitment rates and adherence to follow-up schedules. The Principal Investigator shall permit and assist the monitor to carry out verification of completed eCRFs against data in the source documents.

The Principal Investigator can delegate tasks to his/her personnel, however the role and period of involvement for each clinical site personnel must be documented on the delegation log. Training for all delegated site personnel will be documented on the training log before any involvement with the clinical investigation.

The monitor shall inform the sponsor about any problems relating to facilities, technical equipment, or medical staff at the clinical investigation site. During the clinical investigation, monitors shall check that appropriate written informed consents have been obtained. The monitor shall also be responsible for notifying such deficiencies in writing to the Principal Investigator and convene with the clinical investigation site personnel appropriate and timely corrective actions.

The sponsor, or delegate, will provide clinical monitoring, including review of eCRF with verification to the source documentation, as defined in the monitoring plan. The monitor shall make written reports to the sponsor, after each visit and provide written action items if any, to the Principal Investigator or clinical investigation site personnel.

Periodic monitoring visits (remote or on-site) will be performed as soon as reasonable possible, after the site has enrolled the first subject in the investigation. A final monitoring visit will be performed after all subjects on site have completed the investigation.

A remote, centralized review of the data entered in the eCRF, will be performed by Coloplast CM throughout the conduct of the investigation. See section 9.3.

9.4 Source data verification

A source document is a document in which data collected for a clinical investigation is first recorded. This data is usually later entered in the eCRF. Source documents are defined as "original documents, data, and records". Source documents contain source data, which is defined as all information in original records and certified copies of original records of clinical findings, observations, or other activities in a clinical trial necessary for the reconstruction and evaluation of the clinical investigation.

All documents and data related to the clinical investigation handled by site personnel, shall be produced, and maintained in a way that assures reliability, integrity, control, and traceability, and shall be appropriately stored to provide a complete history.

The Principal Investigator shall ensure the accuracy, attribution, completeness, legibility, and timeliness of the data reported to the sponsor in the eCRFs and in all required reports. All printed copies of electronic source documents shall be certified, as indicated by a dated signature by the investigational site personnel at the time the document is printed. Special requirements should be applied to the capture, review, and retention of electronic source data, to ensure reliability, quality, integrity, and traceability.

The data reported in the eCRFs shall be derived from source documents and be consistent with these source documents, and any discrepancies shall be explained in writing. In some cases, the eCRF can serve as the source document and this must be documented on the Source Data Specification Form. The Source Data Specification Form must be completed at the initiation visit detailing the location of the source data for each data point.

Only the Principal Investigator, or designee, and the sponsor representatives will have access to all the eCRFs.

9.5 Remote monitoring

Remote or centralized monitoring is a remote evaluation carried out by sponsor personnel or representatives (e.g., data management personnel, statisticians, or clinical monitors) at a location other than the site(s) at which the clinical investigation is being conducted. Remote monitoring processes can provide many of the capabilities of on-site monitoring as well as additional capabilities.

In addition to onsite monitoring visits, remote monitoring of the data entered in the e-CRF system could be used to achieve the following:

- Conduct activities such as: standard checks of range, consistency, and completeness of data and checks for unusual distribution of data, such as too little variance.
- Special attention will be given in case of frequent data anomalies or errors, protocol violations or excessive dropouts.
- Augment on-site monitoring by performing monitoring activities that can only be accomplished using centralized processes (e.g., statistical analyses to identify data trends not easily detected by on-site monitoring).
- Monitor data quality through routine review of submitted data in real-time to identify missing data, inconsistent data, data outliers, and potential protocol deviations that may be indicative of systemic and/or significant errors in data collection and reporting at the site.
- Verify source data remotely, provided that both source data and eCRFs can be accessed remotely.
- Conduct aggregate statistical analyses of study data to identify subject data that are outliers relative to others and to evaluate individual subject data for plausibility and completeness.
- Conduct analyses of site characteristics, performance metrics (e.g., high screen failure rates, high
 frequency of eligibility violations, and delays in reporting data), and clinical data to identify early on
 corrective actions needed for characteristics correlated with poor performance or noncompliance.

10 Statistical considerations

All baseline assessments, endpoints and other measurements will be reported by descriptive statistics and/or listed. Summaries will be presented by treatment i.e., investigational or comparator device and if relevant, by other grouping variables.

Descriptive statistics for continuous variables are presented with N, Mean, SD (standard deviation), Median, Min and Max), where N denotes the number of subjects contributing with non-missing data. For discrete variables, descriptive statistics are presented with N and percentage, where percentage is based on the total number of subjects/observations with non-missing data.

A significance level of alpha equal to 0.05 (two-sided) is applied and due to the exploratory nature of this investigation, no procedures for multiplicity control or adjustment of error probabilities will be applied.

Adverse events will be listed and/or summarized. Device deficiencies and concomitant medication will be listed as well.

10.1 Definition of analysis populations

Intention to Treat (ITT), Safety and Per Protocol (PP) populations will be defined at a formal data review meeting before database lock. As a minimum, the data manager, the clinical manager and the statistician will be involved in the classification of subjects.

The Safety population (basis for the AE summary) will include subjects with valid informed consent.

The ITT population (Full analysis set) will be constituted by all randomized subjects, with valid informed consent, who have been exposed to at least one product, and with recorded information on at least one endpoint (non-missing).

Due to the explorative nature of this investigation, no formal PP population is planned. However, if deemed necessary, a PP population will be established, based on a subset of the ITT population.

Individual endpoints/data points may be excluded from analysis, even though the corresponding subject belongs to the ITT and/or PP population. Any exclusion of subjects or data points from any of the populations must be documented.

All analyses will be based upon the ITT population and AEs will be summarized based on the safety population.

The Safety population will include all subjects who have given informed consent.

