7.2.2 Study visits (V1, and V2)

NOTE: All urine volumes (including pre-catheterization residual volumes) will be measured in the same manner throughout the study.

Day 1 (Visit 1):

- Evaluation of Inclusion/Exclusion criteria, including the assessment of any ongoing, active, symptomatic UTI (assessed by Investigator)
- Collection of demographic and baseline data

- Randomisation
- V1-1: A baseline urine sample pre-cystoscopy is collected for the following examination:
 - Dipstick for pregnancy (positive/negative)
 - Dipstick for haematuria (positive/negative)
 - Negative
 - Negative
 - Non-haemolysed 10Ery/ul (+/-)
 - Haemolysed 10Ery/ul (+/-)
 - Positive
 - Non-haemolysed 80 Ery/ul (2+)
 - Haemolysed 25 Ery/ul (1+)
 - Haemolysed 80 Ery/ul (2+)
 - Haemolysed 200 Ery/ul (3+)
- V1-2: The 1st cystoscopy is performed, where the scope is positioned at the centre of the bladder and 6 adjacent images of the dome, posterior wall, and trigone are filmed/photographed to create a naïve bladder map. Cystoscope is inspected for visual blood.
- Collection of concomitant medications. Prophylactic antibiotics should be provided as one time treatment at first visit.
- Collection of adverse events, if applicable

Day 2 (Visit 2):

- V2-1: Urine from a natural void will be collected pre-catheterization. Once the urine sample is obtained, urine volume(mL), RBC and WBC will be evaluated. Haematuria will also be evaluated via dipstick.
- V2-2: Catheterization with either a micro-hole zone- or a 2-eyelet catheter (depending on the randomization). Upon first catheter placement, residual volume pre-catheterization is recorded. Hereafter, the bladder is filled with 250mL (at intervals of 50mL/min) of saline water followed by bladder drainage via the catheter. The catheter is rotated to release any mucosal suction during emptying. Once fully emptied, the catheter is rotated once more to ensure all catheters are being rotated at some point during emptying. The bladder is again filled with 250mL (at intervals of 50mL/min) of saline water followed by bladder drainage and rotations. This procedure is repeated 6 times using the same technique and equipment. The catheter is inspected for visual blood.
- V2-3: The subject will be provided water to drink and the urine from a natural void will be collected.
 Once the urine sample is obtained, urine volume(mL), RBC and WBC will be evaluated Haematuria will also be evaluated via dipstick.

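### Minor: the Safety population is defined by consent alone, so a by-device adverse event table would include never-catheterised subjects and events that precede any device contact

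*Combined protocol and SAP*

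**What the plan says.** Section 10.1 defines the Safety population twice, both times by consent only: "The Safety population (basis for the AE summary) will include subjects with valid informed consent", and at the end of the section, "The Safety population will include all subjects who have given informed consent". It also states that "AEs will be summarized based on the safety population". In the same section the ITT population does require exposure to a product.

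Section 10 gives the general layout rule: "Summaries will be presented by treatment i.e., investigational or comparator device and if relevant, by other grouping variables". For AEs its own sentence is looser: "Adverse events will be listed and/or summarized". Percentages follow a general rule, "where percentage is based on the total number of subjects/observations with non-missing data", which does not say how subjects who leave early are counted.

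On timing, section 7.2.2 and Table 7-1 place randomisation and the first cystoscopy at Visit 1. Section 7.2.2 adds: "Prophylactic antibiotics should be provided as one time treatment at first visit". The study catheter first appears at V2-2: "Upon first catheter placement, residual volume pre-catheterization is recorded". Table 7-1 marks AE collection at every step from V0 to V2-4, but marks device deficiencies only from V2-2.

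**The concern.** Read together, section 10.1 and the general rule in section 10 lead naturally to an AE table with one column per device, built on everyone who consented. Screen failures would have no column, because section 7.2.1 says they are not randomised. Two other groups would be placed under a device:

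- subjects randomised at Visit 1 who leave before V2-2, who add to the denominator without ever meeting the catheter;
- events that follow the first cystoscopy or the antibiotic but precede the catheter, which add to the numerator.

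No section adds an exposure condition or an onset window. At stake is whether a device's column describes that device. Catheter-phase AE rates would be understated if anyone left early, all-AE rates could move either way, and a real difference between the catheters would look smaller.

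**Working it through.** **The plan's own figure.** Section 6 gives 40 completers and 20% drop-out: 40/(1 − 0.20) = 50. This reproduces the stated 50.

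**Inputs.**
- 50 is the number enrolled (section 6), and enrolment means consent (section 6.3). Screen failures are not randomised (section 7.2.1), though they may be replaced (section 6.4).
- The synopsis sets a floor of 20 assigned per product. Section 10.4 aims for 20 completers per group and accepts 18.
- Assumption: all 50 are randomised, 25 per arm.
- The documents give neither the timing of drop-out nor any AE rate. Those used below are assumed.

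**Denominator.** For AEs that arise in the catheter phase, the tabulated rate equals the rate among catheterised subjects multiplied by catheterised/randomised. With 25 randomised in the arm:

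| Situation before V2-2 | Factor in the arm |
|---|---|
| Nobody leaves | 25/25 = 1.00 |
| 1 leaves | 24/25 = 0.96 |
| 2 leave | 23/25 = 0.92 |
| 3 leave | 22/25 = 0.88 |
| 5 leave (all 10 drop-outs, split 5:5) | 20/25 = 0.80 |
| 7 leave (arm falls to the section 10.4 minimum) | 18/25 = 0.72 |
| 10 leave (all drop-outs in one arm) | 15/25 = 0.60 |

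Pooled over arms, three other cases:
- half of the 10 drop-outs leave early: 45/50 = 0.90;
- 5 are screen failures and 5 leave early: 40/45 = 0.89;
- all 10 are screen failures: 40/40 = 1.00.

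**Direction for all AEs.** Take 20 catheterised of 25 randomised, two of them with a catheter-phase AE. The rate among the catheterised is 2/20 = 10.0%. If no early leaver has an AE, the consent-based table shows 2/25 = 8.0%. If one early leaver has a pre-catheter AE, it shows 3/25 = 12.0%.

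**Pre-catheter events in both arms.** Let q be the share of each arm with an earlier AE and p the catheter-phase rate. Assume that the two are independent and that everyone is catheterised. The tabulated rate is 1 − (1 − q)(1 − p). With assumed p of 10% and 30%:

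| q | Tabulated rates | Difference | Ratio |
|---|---|---|---|
| 0 | 10.0% vs 30.0% | 20.0 points | 3.0 |
| 5% | 14.5% vs 33.5% | 19.0 points | 2.31 |
| 10% | 19.0% vs 37.0% | 18.0 points | 1.95 |
| 20% | 28.0% vs 44.0% | 16.0 points | 1.57 |

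If p is the same in both arms, the tabulated rates are also the same. Equal background events therefore create no false difference in expectation, but they shrink a true one.

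**The case against.** **The plan does not commit to a by-device AE table.** The AE sentence in section 10 permits a listing alone and does not mention device, and a consent-based set suits a listing well. This stands, and it makes the point conditional. It does not remove the point, because section 10.1 says AEs will be summarised and the general rule for summaries is by device.

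**Other provisions limit the damage.** Populations are settled at a data review meeting before lock. Table 7-1 records AEs by visit step. Section 20.2 has device-related events marked as related or possibly related. These reduce the consequence, but none sets an exposure or onset rule, and a listing does not correct a table's denominator.

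**Counting all events is consistent with the AE definition.** Section 20.1 covers events whether or not they relate to the device or the procedures. That supports collecting and listing everything from consent. It does not support attributing everything to a device column.

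**Stronger readings that a reader might infer.**
- That the consent-based set is itself an error. It is not: AEs are collected from consent, and the set fits a full listing.
- That the table would favour one catheter. The pre-catheter procedures are the same in both arms, and nothing in the documents says in which arm early leavers would fall.
- That 0.80 is the worst case. It is so only for an even split of the planned drop-out.
- That onset time on Day 2 is not captured. The AE form is not in the documents, so this is unknown.

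**Conclusion.** The concern holds as a minor point, conditional on a by-device AE summary. In that case the rule in section 10.1 places never-exposed subjects and pre-device events in a device's column.

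The size cannot be fixed from the documents. There is no effect if nobody leaves between randomisation and V2-2 and no early AE occurs. Under the assumption of 25 randomised per arm, the factor on catheter-phase rates is 0.80 when all planned drop-out is early and evenly split. It is 0.72 or 0.60 in one arm under the uneven splits shown; the last leaves that arm below the section 10.4 minimum. The attenuation figures rest wholly on assumed AE rates.

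The weight stays low. The trial is exploratory, AEs are descriptive and not a tested endpoint, and the primary analysis uses a population that already requires exposure.

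**What to change.** In section 10.1:

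- keep the consent-based set for the full AE listing, including screen failures;
- base any by-device AE summary on subjects catheterised at V2-2, counting events from the start of V2-2;
- show earlier events separately, using the visit steps already in Table 7-1;
- report the numbers consented, randomised and catheterised.

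The cost is a short wording change, plus a check that the AE form records onset relative to V2-2. That check is needed because V2-1 and V2-2 fall on the same day. AE percentages may move in either direction. No event is lost, since all remain in the listing. One limit remains: the second cystoscopy (V2-4) follows the catheterisation, so its events still cannot be separated from those of the catheter.
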